10.1 Sample Size Determination

A total sample size of 672 subjects (224 per trial arm, and 336 per country) will be necessary to achieve 90% power to detect a non-inferiority margin difference of 15%, assuming that the standard regimen failure rate is 10% and the intervention regimen is 12%, for a one-sided Z test at a significance level of 0.025. This total sample size has been increased in anticipation in 40% to assure a minimum 60% of participants with active infection (positive PCR) and further by 10% to account for potential losses to follow-up, in order to maintain the specified power and inferiority/superiority margins. This means that individuals removed from the study for the reasons mentioned will not be replaced. This sample size will allow the study to also demonstrate a superiority margin of difference of 10% with 80% power regarding the safety of the experimental arm. Considering the percentage of treatment interruption for conventional treatment of 20%, and a reduction of 50% in the experimental arm, power of 90% and $\alpha=0.05$, 197 patients will be needed in each arm.

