10.3 Statistical Analyses

Categorical variables will be presented as frequencies and percentages and continuous variables as median (interquartile range) or mean (standard deviation) according to the data distribution. Normality of distribution will be checked through histograms and the Kolmogorov-Smirnov test.

The chi-squared test or Fisher exact test will be performed to compare the frequencies across categorical variables and the Mann-Whitney test or Student t-test will be used to compare the continuous variables. Intention-to-treat analysis will be performed to evaluate the efficacy and safety that includes all participants randomized to the study groups. The primary analysis will compare proportion of patients with sustained negative PCR at 24 months in their randomly assigned treatment groups (intention-to-treat analysis). Moreover, the proportion of participants with adverse drug events will be also compared. Comparison analyses between groups will be performed using generalized linear models with a log-link

and binomial distribution. Longitudinal differences on quality-of-life scores between groups will be fitted using linear mixed models.

A per protocol analysis will also be performed. Those participants who do not comply with treatment or permanently interrupt or modify the proposed treatment will be excluded from the analysis unless they had a positive PCR prior to that time-point, in which case they will be included in the analysis and considered as a treatment failure.

For PCR analyses, means and bilateral 95% confidence intervals will be presented by group and visit. In addition, time to sustained parasite clearance until 6, 12, 18 and 24 months of follow-up visits will be assessed using Kaplan–Meier survival analysis with log rank test for significance. Repeated measures analysis will also be performed.

Statistical significance will be set at 0.025 for the non-inferiority outcome (positive PCR) and 0.05 for the superiority outcome (percentage of adverse drug reactions and QOL).

The interim analysis for early stopping will be based on superiority and conducted when all participants have reached 12 months of follow up since the end of treatment. An independent data and safety monitoring board (DSMB) will be convened for this study with expertise in CD, clinical trials as well as biostatistics. The purpose of the DSMB is to analyze the preliminary data at 12 months to help in the decision of interrupting any arm.

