A control event rate is expected to be 10% of treatment failure (at least one positive PCR during follow up period) and a 20% of treatment withdrawn due to any AE. Control arm showing posterior probability of superiority of 97.5% or higher will be considered superior. This will be calculated for the experimental intervention versus the control group based on the observed data at the time of interim assessment with a superiority p-value stopping boundary of 0.010.

The decision for interim analysis will be made in a blinded manner (e.g., based on pooled number of events).

All analyses will be performed using Stata 13.0 for Windows.

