10.4 Justification of Non-Inferiority Margin

A non-inferiority margin of 15% has been defined for our study. This means that a maximum acceptable difference in treatment failure rate of 15% with the comparator is considered the difference that would still result in a significant proportion of participants treated appropriately. Historical data on therapeutic failure in most randomized controlled trials is around 20% where the effectiveness rates were measured by parasitic DNA detection on peripheral blood. In adults the failure rate ranges between 10 and 40%. (30,31) If the placebo is considered, it would still be much more advantageous, since the failure rates range between 85 and 95%. (16,32)

For these reasons the study prefers to be conservative in choosing the non-inferiority margin, as the consequence of choosing a margin greater than the actual effect of the active control treatment in the study can be a false conclusion that a new regime is effective, and therefore have an undesirable result for public health. As the intention is treating participants with CD as a public health strategy for reducing the transmission of congenital transmission, reducing parasitemia, through an increase in adherence, a higher rate of compliance in addition to a reduction in costs programmatic level is intended.

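### Section 10.3 names a risk-ratio model for the between-arm comparison, but the 15% margin is an absolute difference, and nothing connects the two

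*Protocol*

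**What the plan says.** Three parts of the protocol bear on the primary test.

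- **Margin (10.4).** Non-inferiority is defined by "a maximum acceptable difference in treatment failure rate of 15% with the comparator".
- **Sample size (10.1).** The trial is sized for 90% power against a 15% margin with failure of 10% (standard) and 12% (short arm), "for a one-sided Z test at a significance level of 0.025".
- **Analysis (10.3).** "The primary analysis will compare proportion of patients with sustained negative PCR at 24 months", by intention to treat. After a sentence on adverse drug events, the section adds: "Comparison analyses between groups will be performed using generalized linear models with a log-link" and a binomial distribution. No endpoint is exempted.

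The other methods in 10.3 are "The chi-squared test or Fisher exact test will be performed to compare the frequencies across categorical variables", a log-rank test for time to clearance, and an instruction that for PCR "means and bilateral 95% confidence intervals will be presented by group and visit". The section calls the outcome sustained negative PCR in one place and positive PCR in another; failure is described as "at least one positive PCR during follow up period".

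A difference-scale decision rule is written out only in 10.11, for the joint Bayesian analysis with the Argentine trial. That rule uses a 20-point margin and a 12-month endpoint.

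**The concern.** The exponentiated treatment coefficient of a log-link binomial model is a risk ratio. Taken alone, it does not test a 15-point difference, and the protocol offers no ratio margin to set it against. The other listed methods do not fill the gap: chi-squared, Fisher and log-rank test equality, and the PCR intervals describe each arm at each visit rather than the contrast between arms.

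If the model's own estimate became the primary result, it could be compared with the margin only after a conversion that depends on the control failure rate. Section 10.1 assumes 10% for that rate, while 10.4 cites about 20% in most trials and 10 to 40% in adults. The conversion would then be chosen after the protocol was fixed, and so would the coding (failure or clearance), which matters on a ratio scale and not on a difference scale.

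**Working it through.** **1. The plan's own sample size.** Inputs from 10.1: failure 10% and 12%, margin 15 points, one-sided 0.025, power 90%.

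n = (1.96 + 1.2816)² × (0.10×0.90 + 0.12×0.88) / (0.15 − 0.02)² = 121.6, so 122 evaluable per arm.

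Allowing for 60% PCR-positive and 10% loss: 122/0.6 × 1.1 = 223.7, so 224 per arm and 672 in total. The stated figure reproduces exactly, with 15% read as an absolute difference.

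**2. The margin as a ratio.** With control failure c, 15 points equals a failure ratio of (c + 0.15)/c and a clearance ratio of (0.85 − c)/(1 − c).

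| Control failure | Failure ratio | Clearance ratio |
|---|---|---|
| 10% | 2.5 | 0.833 |
| 20% | 1.75 | 0.8125 |
| 40% | 1.375 | 0.75 |

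**3. Two data sets with almost the same failure ratio.** 224 per arm, control against short arm, 95% Wald intervals.

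| Failures | Failure ratio | Clearance ratio | Difference (points) | 15-point rule |
|---|---|---|---|---|
| 22 v 34 | 1.545 (0.934 to 2.556) | 0.941 (0.877 to 1.009) | 5.4 (−0.75 to 11.5) | met |
| 45 v 69 | 1.533 (1.106 to 2.126) | 0.866 (0.776 to 0.966) | 10.7 (2.7 to 18.7) | not met |

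The data set with the higher upper limit for the failure ratio passes, and the one with the lower limit fails. Miettinen-Nurminen upper limits (11.6 and 18.7 points) give the same decisions.

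**4. Where the 15-point rule switches.**

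| Failures | Upper limit of difference | 15-point rule | Failure-ratio upper limit | Clearance-ratio lower limit |
|---|---|---|---|---|
| 22 v 41 | 14.87 | met | 3.02 | 0.840 |
| 22 v 42 | 15.36 | not met | 3.09 | 0.835 |
| 45 v 60 | 14.52 | met | 1.87 | 0.827 |
| 45 v 61 | 14.99 | met | 1.90 | 0.821 |

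No single ratio cut-off reproduces these decisions. With failure coding the switch point moves from about 3.0 to about 1.9. With clearance coding it moves little, but the order still breaks: 0.835 fails (22 v 42) while 0.827 passes (45 v 60).

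**5. The difference derived from the log-link fit.** For 22 v 34, the delta method applied to either coding returns 0.0536 (−0.0075 to 0.1146), with the sign reversed for clearance. This is identical to the direct interval.

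**6. Illustration only: ratio margins converted at 10% control failure.** These margins are assumed and are not in the protocol. Power is at 10% v 12% failure, by normal approximation. For 122 per arm:

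- Difference: SE = √(0.1956/122) = 0.0400; 0.13/0.0400 − 1.96 = 1.29, power 90%.
- Failure ratio below 2.5: SE = √(0.9/12.2 + 0.88/14.64) = 0.366; ln(2.5/1.2)/0.366 − 1.96 = 0.05, power 52%.
- Clearance ratio above 0.833: SE = √(0.1/109.8 + 0.12/107.36) = 0.0450; ln(0.9778/0.8333)/0.0450 − 1.96 = 1.59, power 94%.

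The last two columns give the chance of declaring non-inferiority when the true failure rates are 20% v 35%, exactly at the margin, by full enumeration.

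| Rule | Power, 122/arm | Power, 224/arm | False claim, 122/arm | False claim, 224/arm |
|---|---|---|---|---|
| Difference < 15 points | 90% | 99% | 2.5% | 2.5% |
| Failure ratio < 2.5 | 52% | 78% | 37% | 59% |
| Clearance ratio > 0.833 | 94% | 99.8% | 1.3% | 1.0% |

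**The case against.** The best defence is that the decision scale is already settled. Sections 10.1 and 10.4 both speak of a difference, alpha is fixed, and since no ratio margin exists, the difference is the only non-inferiority test that can be carried out. The log-link sentence is generic and follows the adverse-event comparison. A difference can be obtained from the fit, and the interval method is ordinary SAP content. The primary endpoint is also worded mainly as clearance. On that coding the pair in step 3 sorts correctly: against 0.833, the lower limit 0.877 passes and 0.776 fails. The poor operating characteristics in step 6 need a failure-ratio margin that the protocol never proposes. Finally, 10% is the design assumption; the 20% and 10 to 40% figures are historical.

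Much of this stands. The harm is conditional, the clearance coding is close to harmless, and step 6 is illustrative. Reading the log-link sentence as covering the primary comparison is an inference, though the natural one, since the sentence follows that comparison and excludes nothing.

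What the defence does not remove is that the protocol was not silent. It fixed a model on one scale and a margin on another. If a different primary method was intended, 10.3 does not name it. The design assumption of 10% does not help if the observed control rate differs, and the clearance reordering in step 4 remains.

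**Conclusion.** The concern holds as an inconsistency that should be fixed. Sample size, margin and alpha agree with one another on the difference scale. The named analysis model estimates a ratio, and no step leads from it to the 15-point limit.

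The consequence ranges from nothing (difference derived from the fit) through slight (clearance ratio) to serious (failure ratio, where the equivalent of 15 points moves between 2.5 and 1.375 across the control rates cited in 10.4). This rests on reading the log-link sentence as applying to the primary endpoint. The numerical examples use 224 analysed per arm and Wald limits. The ratio-margin power and error figures rest in addition on margins assumed here.

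**What to change.** Add to 10.3, in place of an unqualified log-link statement for the primary endpoint:

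*The primary estimate is the difference in failure proportion (at least one positive PCR; short arm minus 8-week arm) with a two-sided 95% confidence interval. Non-inferiority is declared if the upper limit is below 15 percentage points.*

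Name one method for the interval: for example Miettinen-Nurminen, an identity-link binomial model, or standardised risks from the log-link model. Report the risk ratio as secondary, and use one outcome coding throughout 10.3.

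The cost is one or two sentences. Sample size, margin, visits and data collection are unchanged, and the planned 90% power at 122 evaluable per arm stands.

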3.1 Assessment of Efficacy

Efficacy of study treatment will be assessed by comparing the parasitological clearance rate, determined by sustained parasitological clearance until 24 months of follow-up after treatment. Secondary assessments of PCR will be conducted at 1, 4, 6, 8, 12 and 18 months

As this is a double-blind study, this will not interfere with the schedule of events, since all participants will have all required samples planned at each visit. In addition, a qualitative and quantitative efficacy assessment will be performed, correlating incidence of and time to parasitological clearance with changes in *T. cruzi* serology.

The study manual of operations will provide full details regarding procedures for blood samples (tube types and number, aliquots volume), handling, storage, and shipment of the samples for laboratory evaluation. Quality assurance systems will be in place and described. Training of personnel in each of the activities described above will take place before initiation of this clinical trial. All parasitological and other

laboratory assessments will be performed blinded to treatment allocation. The PCR samples will all be evaluated by trained specialists in a central laboratory in each country, using harmonized protocols, and similar techniques. Quality control will be carried out in the two countries by the same team of molecular biology specialists.

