5.1 Eligibility criteria

5.1.1 Inclusion Criteria

- Adults aged ≥ 18 years;¹
- CD diagnosis through the positivity of two serological tests that use different antigens (recombinant and native antigens, according to World Health Organization (WHO) recommendations) (28).
- Informed consent form read and signed by the participant.
- Weight ≥ 50 kg to ≤ 95 kg.
- Ability to carry out all tests and visits to the protocol site and have a fixed address.
- Women of childbearing age should have a negative urine or serum pregnancy test at baseline.

¹ It is considered that neither the dynamics of parasitemia, nor the therapeutic response and safety profile, demonstrate differences in the chronic phase adult population up to 60 years of age. Considering that there is no contraindication for administering antiparasitic treatment beyond 60 years of age, and that the objective is to see the antiparasitic effect and the safety profile, recruiting patients older than 60, which will allow a greater probability of recruiting patients in the shortest possible time, optimizing studytimes, financial resources, and the opportunity to have the results available.

A contraceptive method should be used.²

Note that although PCR will be determined at baseline, this will not be considered as an inclusion criterion.

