6.6 Treatment assignment

This is a double-blind trial in which neither the participant nor the investigators will know the duration of treatment that has been assigned to each participant. At the moment of the inclusion a consecutive numeric code will be generated. That number will be linked with a randomization code that will correspond to the treatment kit number. That number will never reveal the therapeutic branch designation. Each center will have a randomization list with the inclusion number and the kit number, and a randomization closed envelope which links the kit number with the treatment. To avoid bias in the allocation of treatment groups, randomization will be centralized, and investigators will not have access to the sequence of allocation. Participants will be randomized 1:1:1 to each of the treatment arms and balanced by country.

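### The primary comparison names neither country, which balances the randomisation, nor the baseline PCR result; using both is a free but small gain in precision

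*Protocol*

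**What the plan says.** **Allocation.** Protocol section 6.6: "Participants will be randomized 1:1:1 to each of the treatment arms and balanced by country". Section 10.1 gives "A total sample size of 672 subjects (224 per trial arm, and 336 per country"; section 10.11 gives 112 per country and arm.

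**Endpoint measurement.** Under section 3.1, PCR samples are evaluated "in a central laboratory in each country", with harmonised methods and one quality-control team for both countries. Section 7 adds a harmonisation panel, and section 22 lists discrepant PCR results among the anticipated problems.

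**Baseline PCR.** Section 8.1 has it taken from all participants at screening. Section 5.1.1: "Note that although PCR will be determined at baseline, this will not be considered as an inclusion criterion". Section 10.1 enlarges the sample so that at least 60% are PCR-positive. Section 10.6 lists the proportion positive as a baseline description.

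**Primary comparison.** Sections 10.3 and 10.8 compare sustained negative PCR at 24 months by randomised arm, by intention to treat. Section 10.3 names chi-squared or Fisher tests and then states: "Comparison analyses between groups will be performed using generalized linear models with a log-link" and a binomial distribution. No covariate is named. The only multivariable work for this trial alone is a search for predictors of response in 10.8 (p<0.20 screen, then backward elimination). Country-specific parameters appear only in the joint analysis with the Argentine trial (10.11).

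**The concern.** A factor used to balance allocation is normally carried into the analysis. Otherwise the standard error includes between-country variation that the design has already removed from the treatment contrast. Here country also coincides with the laboratory that reads the endpoint, so detected failure could differ by country. Baseline PCR is not a balancing factor, but it is an earlier measurement of the quantity that defines the endpoint, and section 10.1 allows for up to 40% of participants being negative.

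At stake is a slightly wider interval against the 15-point margin than the design could deliver. There is also a gap in pre-specification: if adjustment were added after the data were seen, it would look data-driven, and the only covariate procedure on the page is a stepwise search.

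**Working it through.** **1. Reproduce the stated sample size.** Section 10.1 aims to "achieve 90% power to detect a non-inferiority margin difference of 15" percentage points, "assuming that the standard regimen failure rate is 10% and the intervention regimen is 12" percent, "for a one-sided Z test at a significance level of 0.025". With unpooled variance:

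n = (1.960 + 1.282)² × (0.10×0.90 + 0.12×0.88) / (0.15 − 0.02)² = 10.51 × 0.1956 / 0.0169 ≈ 122 per arm.

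122 / 0.60 × 1.10 = 223.7, hence 224. The stated figure reproduces as an unstratified two-group calculation.

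**2. Variance removed by country.** Country rates are not in the protocol; assume 5% v 15%, equal numbers.

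- Within-country: (0.05×0.95 + 0.15×0.85)/2 = (0.0475 + 0.1275)/2 = 0.0875
- Ignoring country: 0.10×0.90 = 0.0900
- Ratio 0.972: variance 2.8% smaller, standard error 1.4% smaller (√0.972 = 0.986)

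**3. Variance removed by baseline PCR.** Assume 60% positive, failure 15% in positives and 2% in negatives.

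- Within-stratum: 0.6×0.1275 + 0.4×0.0196 = 0.0843
- Ignoring PCR: overall failure 0.6×0.15 + 0.4×0.02 = 0.098, so 0.098×0.902 = 0.0884
- Ratio 0.954: variance 4.6% smaller, standard error 2.3% smaller
- In participants: 224 × (1/0.954 − 1) ≈ 11 per arm

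**4. Effect on the interval.** At 10% v 12% and 224 per arm, the 95% half-width is 1.96 × √(0.1956/224) = 5.8 points. A standard error 1.4% or 2.3% smaller narrows it by about 0.08 or 0.13 points, against a margin of 15.

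**5. Operating characteristics.** Simulation of the non-inferiority test on the risk difference, 200,000 trials per scenario, size-proportional weights. Country control rates were varied from 10%/10% to 2%/18%. Type I error is taken at a true difference of 15 points.

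| Per country and arm | Quantity | Unstratified | Stratified by country |
|---|---|---|---|
| 112 | Type I error | 2.6% to 2.4% | 2.6% to 2.7% |
| 112 | Power | 99.2% to 99.3% | 99.2% to 99.4% |
| 61 (= 122/2) | Power | 90.1% to 90.8% | 90.2% to 91.8% |

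The slight excess over 2.5% is present in both tests when the countries do not differ, so it does not come from omitting country. As the countries diverge, the unstratified test becomes the more conservative of the two. At the extreme of 2% v 18%, the variance reduction under the design alternative reaches 6.6%.

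For baseline PCR (60% positive with failure 10%/12%; failure in negatives 0% to 5%), variance falls by 1% to 5%. Power is above 99.8% either way at 224 per arm, or at 202 (= 224 × 0.90) after losses.

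**6. Is chance imbalance in baseline PCR an additional harm?** The between-arm difference in baseline positivity has SD √(2×0.6×0.4/224) = 0.046. With the 13-point prognostic gap of step 3, its 95% range moves the failure difference by 1.96 × 0.046 × 0.13 = ±1.2 points. Its share of the unadjusted variance is (0.13×0.0463)² / (2×0.0884/224) = 4.6%, the same 4.6% as in step 3. The unadjusted standard error already contains it.

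**The case against.** The strongest reply is that the protocol is silent on covariates rather than wrong. Section 10.3 names a model family and link, gives no linear predictor and nowhere calls the model unadjusted; both terms could be added without contradicting it. Covariate lists are commonly left to a statistical analysis plan, and section 10.2 refers to one. This stands: a reader might infer that the protocol prescribes an unadjusted primary analysis, and the text does not say so.

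A reader might also infer that separate laboratories bias the comparison. They do not. Arms are balanced within country, so a laboratory difference affects all arms alike, and the stated harmonisation and common quality control reduce it further. Nor is chance imbalance in baseline PCR a second problem: step 6 shows it is the same variance, already covered by the unadjusted interval, and ±1.2 points is a 95% range rather than a maximum.

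The effect is small and depends on assumed rates, and adjusting for a prognostic variable that is not a balancing factor is optional. That also stands. What the reply does not remove is that a somewhat better analysis is available from data already collected, and that section 10.3 goes far enough in naming tests, distribution and link for the factors to be named there too.

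**Conclusion.** A free improvement of minor severity. The primary comparison as written names neither the factor that balances allocation nor a baseline value measured in everyone. It remains valid without them. Under the assumed rates, variance falls by about 3% for country and 1% to 5% for baseline PCR, so the standard error is about 1% to 2% smaller; power moves by about 1 point or less, and 224 per arm is unaffected. The direction is secure; the size rests on rates that the protocol does not give.

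A reader might take baseline PCR adjustment as a cure for a different problem: section 10.1 sizes the trial on PCR-positive participants, while 10.2 and 10.3 analyse all randomised. It is not a cure. With 60% positive, a true difference of 15 points in positives and none in negatives, the overall difference is 0.6 × 15 = 9 points. In the same simulations (202 to 224 per arm), non-inferiority is then declared in 46% to 57% of trials unadjusted and 48% to 61% stratified, against about 2.7% in PCR-positives alone. That mismatch needs its own remedy.

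**What to change.** In Protocol sections 10.3 and 10.8, and in the statistical analysis plan, state that the primary quantity is the absolute difference in failure, compared with the 15-point margin, stratified by country and adjusted for baseline PCR status. Use Mantel-Haenszel weights, or a binomial model with both terms standardised to a risk difference, because a log link alone yields a ratio while the margin is a difference. Keep the unadjusted difference as a sensitivity analysis.

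Use country rather than centre. Four centres by PCR status make eight strata; with 56 per centre and arm (224/4, equal centres assumed), 40% negative and 2% failure, each PCR-negative cell expects 56×0.4×0.02 = 0.45 failures per arm. By country it is 112×0.4×0.02 = 0.9. That is still thin, so Mantel-Haenszel weighting is the safer choice if negatives have almost no failures.

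The cost is one sentence in each place, with no new data and no change in sample size. It should be fixed before any unblinded outcome data are seen, including those for the 12-month interim analysis.
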